5.3. Inclusion and Exclusion Criteria

Inclusion Criteria - Radical Prostatectomy groups

The participant must satisfy all the following criteria to be eligible for the study:

- Histologically confirmed adenocarcinoma of the prostate
- Clinically localised or locally advanced disease deemed operable by the treating consultant urological surgeon *i.e.:*
 - Gleason score ≤ 7
 - Local tumour stage $\leq T3c$ and deemed operable
 - No evidence of metastases (Nx/N0 and Mx/M0)
 - No evidence of high grade Gleason 5 disease
 - PSA ≤ 20 ng/ml
- Scheduled for and considered fit for radical prostatectomy
- Absence of any indication to perform urgent surgery that would not allow completion of the study interventions prior to radical prostatectomy

Inclusion Criteria - Metastatic prostate cancer groups

The participant must satisfy all the following criteria to be eligible for the study:

- Histologically confirmed adenocarcinoma of the prostate cancer. Note, any Gleason grade or primary tumour staging at diagnosis is permitted.
- Evidence of at least one distant metastasis based on MRI, CT, PET or bone scintigraphy.
- Established on and suitable to continue with androgen deprivation therapy (ADT) using any luteinizing hormone releasing hormone (LHRH) agonist. LHRH agonist therapy may include goserelin (Zoladex®), leuprorelin acetate (Prostap®) or any other licenced product in this class.
- On treatment with anti-androgen therapy using either abiraterone (Zytiga®) or enzalutamide (Xtandi®) and demonstrating evidence of disease progression at the time of enrolment, defined according Prostate Cancer Working Group 3 Criteria as either:
 - PSA progression as defined by a minimum of 3 rising PSA levels with an interval of ≥ 1 week between each assessment where the PSA value at screening should be ≥ 2 ng/mL *or*;
 - progressive nodal or visceral disease *or*;
 - progressive bone metastases

Upon enrolment in the study, the treatment with abiraterone or enzalutamide will be discontinued.

- An archival specimen of tumour tissue should be available; if not, an on-study fresh tumour biopsy must be obtained prior to the first study treatment.
- Patients who have received chemotherapy following progression on androgen-targeting therapies are eligible
- Satisfactory functional status defined as Eastern Cooperative Oncology Group (ECOG) Performance Status ≤ 1

Inclusion Criteria – All participants

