6. TREATMENT OF STUDY SUBJECTS

6.1. Study visits

The study visits and administration of investigational therapies will be undertaken by an adequately qualified and trained member of the team of investigators. Each visit is assigned a time point and a window period, within which the visit will be conducted. These can be found in the schedule of attendances (Appendix 1).

Screening visit

All potential participants will have a screening visit, which may take place up to 4 weeks prior to the first study procedure. Informed consent will be taken at screening prior to any study-specific procedures being carried out, as described in section 5.2. If consent is obtained, the screening procedures indicated in the schedule of attendances will be undertaken. A baseline medical history, physical examination and assessment of performance status will be performed. Vital signs will be recorded and urinalysis will be performed. Inclusion and exclusion criteria will be checked. Blood will be drawn for clinical haematology and biochemistry, HIV, Hepatitis B and Hepatitis C serology, PSA, exploratory biochemistry and ctDNA. Subjects will be counseled by one of the investigators prior to HIV, Hepatitis B and Hepatitis C testing.

Potential subjects will be informed that blood samples, as well as the surgical specimens from radical prostatectomy and archival biopsy samples that are collected as standard of care or newly obtained on-study tumour biopsy samples will be used for research purposes. They will be informed that after study investigations are completed, any surplus samples of blood (and/or surgical or biopsy material) may be stored for possible future ethically approved research,

including for example exploratory immunology, and genotypic testing of genetic polymorphisms potentially relevant to vaccine immunogenicity. Subjects will be able to decide if they permit such future use of any unused or surplus samples. If a subject elects not to permit this, all of that subject's leftover samples will be discarded at the end of the study to meet Good Clinical Practice (GCP) and regulatory requirements.

The eligibility of the subject will be reviewed at the end of the screening visit and again when all results from the screening visit have been considered. If eligible, a week 0 enrolment visit will then be scheduled.

Subsequent Visits

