At each subsequent study visit the ongoing eligibility of the volunteer will be reviewed. Vital signs will be recorded, urinalysis performed, ECOG performance status assessed and if necessary, a medical history and physical examination may be undertaken to determine any relevant interval changes in the participants health. In the event of new clinical or laboratory findings, study procedures involving administration of investigational vaccines or intravenous checkpoint inhibitors may be postponed according to criteria in Section 5.5. All blood tests should be taken prior to administration of any study therapies.

Group 1

Day 0: Enrolment, ChAdOx1.5T4 priming vaccination visit

Subjects will not be considered enrolled in the study until they have received the first study vaccination with ChAdOx1.5T4 on Day 0. Prior to vaccination, blood tests will be taken as detailed in the schedule of attendances (Appendix 1). Following intramuscular administration of the ChAdOx1.5T4 vaccine, the injection site will be covered with a sterile dressing and the patient will stay under observation, in case of immediate adverse events. Observations will be taken 60±15 min after vaccination and the sterile dressing removed and injection site inspected. A diary card, oral thermometer and tape measure will be given to each participant to solicit the following adverse events:

- Localised adverse events
 - o Diameter of redness at vaccination site
 - o Diameter of swelling at vaccination site
 - o Pain, warmth and erythema at the vaccination site

- Systemic adverse events
 - o Recorded temperature and pyrexial episodes
 - o Feverishness
 - o Headaches
 - o Fatigue
 - o Nausea
 - o Generalised muscle aches

- o Generalised joint aches

Day 7: MVA.5T4 boost vaccination visit and first checkpoint inhibitor therapy

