8.2. Assessment of Adverse Events

Adverse Event (AE)

An AE is any untoward medical occurrence in a volunteer, which may occur during or after administration of an Investigational Medicinal Product (IMP) and does not necessarily have a causal relationship with the intervention. An AE can therefore be any unfavourable and unintended sign (including an abnormal laboratory finding), symptom or disease temporally associated with the study intervention, whether or not considered related to the study intervention.

Adverse Drug Reaction (ADR)

An AR is any untoward or unintended response to an IMP. This means that a causal relationship between the IMP and an AE is at least a reasonable possibility, i.e., the relationship cannot be ruled out. All cases judged by the reporting medical Investigator as having a reasonable suspected causal relationship to an IMP (i.e. possibly, probably or definitely related to an IMP) will qualify as adverse reactions.

Unexpected Adverse Reaction (UAR)

An adverse reaction the nature and severity of which is not consistent with the product information set out in:

- the summary of product characteristics (SmPC) for products with a marketing authorisation, i.e. nivolumab.
- the Investigator's Brochure (IB) for any other investigational product, i.e. ChAdOx1.5T4, MVA.5T4

Serious Adverse Event (SAE)

An SAE is an AE that results in any of the following outcomes, whether or not considered related to the vaccine:

- Death (apart from death where prostate cancer is certified as the underlying cause)
- Life-threatening event (i.e., the volunteer was, in the view of the Investigators, at immediate risk of death from the event that occurred). This does not include an AE that, if it occurred in a more serious form, might have caused death
- Persistent or significant disability or incapacity (i.e. substantial disruption of one's ability to carry out normal life functions)
- Hospitalisation, regardless of length of stay, even if it is a precautionary measure for continued observation or prolongation of existing hospitalisation

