8.5. Reporting procedures

Reporting Procedures for All Adverse Events

After an eligible participant is enroled onto the study on receipt of the first study procedure, all AEs occurred within 28 days of study treatment and only grade 3 AEs outside this time window will be reported in the study case report forms (CRF), whether or not attributed to study procedures. AEs may be observed by the Investigators or reported by the participant either spontaneously or during diary card monitoring. All AEs that result in a subject's withdrawal from the study will be followed up, with their consent until a satisfactory resolution occurs, or until a non-study related causality is assigned.

Reporting Procedures for Serious Adverse Events

All serious adverse events (SAEs) occurring after an eligible participant is enrolled onto the study on receipt of the first study intervention, will be reported throughout the trial period. All SAEs will be documented accurately and notification deadlines respected. SAEs will be reported on an SAE Report Form to the Sponsor or the Sponsor's delegated representative (Chief Investigator) and the Study Medical Monitor (SMM), according to the relevant SOP within 24 hours of the Investigator becoming aware of them. SAEs will not normally be reported immediately to the ethical committee(s) and MHRA unless there is a clinically important increase in occurrence rate, an unexpected outcome, or a new event that is likely to affect safety of trial volunteers, in the opinion of the Chief Investigator and/or SMM. In addition to the expedited reporting above, the Investigator shall include all SAEs in the annual Development Safety Update Report (DSUR) report. Any updates to relevant information concerning the SAE that becomes available after the SAE initial report has been sent (outcome, precise history, results of investigations, copy of hospital report, etc) will be forwarded in a timely manner using the SAE Update Report Form. For all deaths, any available post-mortem reports and relevant medical reports will be made available for reporting to the relevant authorities. The Sponsor, or a medically qualified investigator delegated by the

Sponsor, is responsible for commencing, maintaining and completing the SAE Sponsor Report Form. The anonymity of subjects shall be respected when forwarding this information.

Expectedness

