Assessment & recording of adverse events		X	X	X	X	X	X	X	X	X
Radiological assessment (bone scintigraphy, CT scan, MR scan)		X ¹								
Patient alert card provided		X								
Diary card provided		B			C			D		
Diary card returned				X				X		
Haematology ²	2	2		2	2		2	2		2
Biochemistry ²	4	4		4	4		4	4		4
Serum glucose ²	2	2		2	2		2	2		2
Thyroid function tests ²⁻³	2	2						2		
PSA ¹	5	5		5	5		5	5		5
Urinalysis	X	X		X	X		X	X		X
HBsAg, HIV &HCV Ab ¹	5									
Human leukocyte antigen typing (ml)				5						
Exploratory immunology (ml)		30		40			40			40
CTC (ml)		8						8		
ctDNA (ml)		8			8			8		

Total blood volume per visit (ml) ²	20	61		58	21		53	31		53
--	----	----	--	----	----	--	----	----	--	----

* Window is based on preceding IMP administration

¹ Window is -28 days

² Volume can vary by site according to local practices

³ Total triiodothyronine (T3) or free T3c, free thyroxine (T4) and thyroid stimulating hormone (TSH)

Group 2: Participants with Metastatic Prostate Cancer

Table of events (part 2 of 2)

Visit/Telephone Call Number	V7	T4	V8	V9	T5	V10	V11	V12	V13
Time from enrolment (weeks+days)	12	12[contact][contact]
Window (days)*	±7	+3	+3	±2	+3	+3	±7	±14	±14
Informed consent									
Review of inclusion/exclusion criteria	X		(X)	X		(X)	(X)	(X)	(X)
Medical history	(X)		(X)	(X)		(X)	(X)	(X)	(X)
Physical examination (if required)	(X)		(X)	(X)		(X)	(X)	(X)	(X)
Telephone Call		X			X				
Recording vital signs	X		X	X		X	X	X	X
ECOG Status	X			X			X	X	X
ChAdOx1.5T4 vaccination	X								
MVA.5T4 vaccination				X					
Nivolumab infusion	X								
Assessment & recording of adverse events	X	X	X	X	X	X	X	X	X
Radiological assessment (bone scintigraphy, CT MR scan)							X		X
Diary card provided	C			B					
Diary card returned	X			X		X			
Haematology ¹	2		2	2		2	2	2	2
Biochemistry ¹	4		4	4		4	4	4	4
Serum glucose ¹	2		2	2		2	2	2	2
Thyroid function tests ^{1, 2}	2			2			2	2	2
PSA ¹	5		5	5		5	5	5	5
Urinalysis	X		X	X		X	X	X	X
Exploratory immunology (ml)			40			40	30	40	40
CTC (ml)							8		
ctDNA (ml)	8						8		
Total blood volume per visit (ml) ¹	23		53	15		53	61	55	55

Cumulative blood volume = 612m¹

* Window is based on preceding IMP administration

¹ Volume can vary by site according to local practices

² Total triiodothyronine (T3) or free T3c, free thyroxine (T4) and thyroid stimulating hormone (TSH)

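### In metastatic patients without archival tissue, serious events arising between the required pre-treatment biopsy and the first vaccination fall outside the SAE reporting window of section 8.5

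*Protocol*

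**What the plan says.** Section 5.3 (inclusion criteria, metastatic groups) asks for an archival tumour specimen; "if not, an on-study fresh tumour biopsy must be obtained prior to the first study treatment". Section 6.1 adds that "newly obtained on-study tumour biopsy samples will be used for research purposes". The Group 2 schedule in Appendix 1 places the fresh biopsy at V1 (week 0) with the footnote "Window is -28 days".

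Section 6.1 states for both groups: "Subjects will not be considered enrolled in the study until they have received the first study vaccination with ChAdOx1.5T4 on Day 0". Section 8.5 then reports all SAEs "occurring after an eligible participant is enrolled onto the study on receipt of the first study intervention". Section 8.2 describes an adverse event as something arising at or after dosing with an investigational product, and an SAE is an adverse event that meets a seriousness criterion. In both Appendix 1 schedules the row for recording adverse events is blank at screening and begins at V1.

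**The concern.** The biopsy is a study procedure. It is done after consent, the protocol requires it when no archival specimen exists, and the sample is used for research. Yet the safety reporting clock starts at the first vaccination, which by the same rule comes later. A bleed, an infection or a hospital admission in between would be a serious consequence of taking part in the trial, but the reporting rules, followed exactly, do not ask for it to be reported.

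What is at stake is oversight, not an estimate. Safety is a co-primary objective in both cohorts, and the trial has 36 men in total. The sponsor, the medical monitor and the DSMC should be able to see serious harm from a procedure that the protocol itself imposes. This is a reporting duty set in the protocol, so a statistical analysis plan could not repair it.

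**Working it through.** The plan states no figure on this point, so the check is to read the passages together.

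| Step | Place | What it fixes |
|---|---|---|
| 1 | Section 5.2, section 6.1 (screening visit) | Consent precedes every study-specific procedure |
| 2 | Section 5.3, metastatic groups | Biopsy before first study treatment if there is no archival tissue |
| 3 | Appendix 1, Group 2, part 1 | Biopsy window of 28 days before V1 |
| 4 | Section 6.1, Group 2, Day 0 | Enrolment is the first ChAdOx1.5T4 vaccination |
| 5 | Section 8.2 | Adverse events, and so SAEs, are tied to dosing |
| 6 | Section 8.5, SAE paragraph | SAE reporting starts after enrolment |
| 7 | Appendix 1, both schedules | Recording of adverse events starts at V1 |

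**Length of the interval.** The biopsy can fall on any day from Day −28 to Day 0. The time not covered is Day 0 minus the biopsy day: at most 0 − (−28) = 28 days, at least 0. The protocol does not say how long it will be in practice.

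**Who is affected.** Only Group 2 men without an archival specimen, so at most the 24 planned for that group. The actual number is not given. The Group 1 schedule also lists a fresh biopsy if required, but no Group 1 criterion in section 5.3 calls for one, so the point is not extended to that group.

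**Four cases under the rules as written.**

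1. Biopsy complication with onset after Day 0 in a vaccinated man: reportable. Section 8.2 counts SAEs whether or not the vaccine is thought to be the cause.
2. Non-fatal serious complication with onset before Day 0, man vaccinated later: onset precedes enrolment and dosing, so it is outside the section 8.5 window.
3. The same complication in a man who is then never vaccinated: he is never enrolled, so the window never opens for him.
4. Death before Day 0: section 8.5 separately sends deaths during the study to the sponsor. Section 4.5 dates the start of the study from the first administration of a study drug. Read for the trial as a whole, this covers a later patient; read for each patient, it does not.

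The gap consists of cases 2 and 3.

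**Do other sections close it?**

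- Section 12.2 has the investigators notify SAEs at the site to the sponsor, but an event before dosing does not clearly meet the section 8.2 definition.
- Section 8.6 mentions decisions not to enrol a subject, but refers back to the adverse event procedures, which have not yet started.
- Section 8.7 bases the updated DSMC reports on enrolled participants. It also lets the investigator seek advice from the chair in any situation, which is discretionary.
- Section 8.3 assesses causality against vaccine and checkpoint inhibitor only.
- Section 4.6 does not list biopsy among the risks to participants.

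None of these gives an explicit route for cases 2 and 3.

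**The case against.** The strongest reply is that starting SAE collection at first dosing is a deliberate and consistent choice: sections 6.1, 8.2 and 8.5 and the Appendix 1 schedules all point to Day 0. The primary safety question concerns the vaccine combined with nivolumab, and an event before any dose says nothing about that. The biopsy is only a fallback, and the interval is short. The wording in section 8.2 on timing is also permissive, and an investigator could inform the sponsor or the DSMC chair anyway.

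Much of this stands. No efficacy or safety estimate is biased, and the affected group may be small. It does not answer the point about oversight: a consistent start date still leaves out a procedure that the protocol requires before that date, and voluntary notification is not a reporting rule.

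A reader might also infer a direct contradiction within section 8.5, because the adverse event paragraph starts from the first study procedure and the SAE paragraph from the first study intervention. The documents do not support that clearly. Section 6.1 places screening up to 4 weeks before the first study procedure, which suggests that the phrase means Day 0. It is loose terminology that needs aligning. If the phrase were meant to include the biopsy, it would conflict with the enrolment definition in section 6.1.

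**Conclusion.** The point holds in a limited form. For Group 2 men without archival tissue, non-fatal serious events with onset between the required biopsy and the first vaccination, an interval of 0 to 28 days, lie outside the section 8.5 window. For a man who is never vaccinated as a result, no explicit route exists apart from the line for deaths.

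A reader might go further and conclude that biopsy harm is never reported, or that the sponsor and DSMC could not learn of it. The text does not support that: events with onset after Day 0 are reportable regardless of cause, deaths have their own line, and informal routes exist. Nor can an expected number of missed events be given, because the protocol states neither the proportion of men needing a fresh biopsy nor a complication rate. It also does not rank biopsy against the other procedures by risk.

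The conclusion assumes that enrolment in section 8.5 has the meaning given in section 6.1. The defect is one of safety oversight and is cheap to correct; it does not alter the primary endpoint.

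**What to change.** - In section 8.5, start the reporting of SAEs related to study-mandated procedures at signed consent, including for men who are never vaccinated. Reporting of all other SAEs can keep its present start at Day 0.
- Use one start point and one term throughout. Reconcile the enrolment definition in section 6.1, the adverse event definition in section 8.2, the two trigger phrases in section 8.5 and the adverse event row in Appendix 1, so that the screening interval is visibly covered for these events.
- Add a CRF flag for relationship to a study procedure, and include flagged events in the DSMC safety reports even when the man was not enrolled.
- Tabulate procedure-related events before Day 0 separately, outside the treatment-emergent primary safety endpoint, so that its definition and denominator do not change.

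The cost is protocol wording, one CRF flag and a few extra reports. Sample size, visits and analyses of the treatment are unaffected.

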8.6. Procedures to be followed in the event of abnormal findings

Abnormal clinical findings from medical history, examination, urinalysis or blood tests at any point in the study will be assessed as to their clinical significance. If a test is deemed clinically significant, it may be repeated, to ensure it is not a single occurrence and further diagnostic investigations carried out to determine any underlying pathology. If a result or finding is persistent or clinically significant, the subject will be informed and appropriate medical care arranged as appropriate and with the permission of the subject. Decisions to exclude the subject from enrolling in the trial or to withdraw a subject from the trial will be at the discretion of the Investigators, following procedures for adverse events as described above.

8.7. Data and Safety Monitoring Committee

A Data and Safety Monitoring Committee (DSMC) will be appointed to provide real-time safety oversight. It will consist of a consultant oncologist, a consultant physician with experience of vectored vaccine trials, a further member with statistical expertise and up to two further members with trial expertise, all of them independent of the study. The DSMC will review all SAEs at the meetings that will be convened following each interim safety report and a narrative from the Chief Investigator at the timepoints as below:

An interim safety report of all recorded events, along with a narrative from the Chief Investigator, will be submitted to the Data and Safety Monitoring Committee for review after the first 6 patients (3 patients with intermediate risk disease and 3 metastatic patients) complete the study treatment and have reached the 24-week timepoint for efficacy assessment. An updated report to the Data and Safety Monitoring Committee, covering all enrolled participants to date will then be triggered when every 6th subsequent participant has reached 24-week timepoint for efficacy assessment.

The DSCM has the power to terminate the study if deemed necessary following a study-related SAE.

The DSMC chair will be notified of SAEs if deemed possibly, probably or definitely related to study-related interventions within 24 hours of the investigators' being aware of their occurrence.

The chair of the DSMC will be contacted for advice and independent review in the following situations:

- Following any SAE deemed to be possibly, probably, or definitely related to the study vaccine.
- Any other situation where the Investigator feels independent advice or review is important.

